9.2.4. Study Enrollment

Investigators who previously participated in trials of patients with GIST, prescribing physicians, and other clinicians with expertise in GIST clinical studies will be approached for participation in this study. Each identified site will be sent a confidentiality agreement and then study information. For those sites interested, a feasibility questionnaire will be sent for completion. Qualified sites with the intended patient population will be selected for the study. To facilitate enrollment into the study, the Sponsor will offer sites additional support as needed within the confines of local regulations and guidelines.

9.3. Variables

The data collection plan is outlined in Table 1. Data will be collected prospectively for patients who initiate or continue to receive treatment with avapritinib. Retrospective data collection will be performed when available. All efforts will be made to ensure that the retrospective data of

patients who discontinued avapritinib treatment previously are of good quality and provide sufficient information on the variables required.

Data of interest include the following:

Demographic data and relevant medical history at the time of the first avapritinib dose:

- Age
- Sex
- Height
- Weight
- Race/ethnicity (in accordance with the local regulations)
- ECOG performance status GIST diagnosis (before the first avapritinib dose according to local standard procedures)
 - Date of diagnosis
 - Primary tumor site (e.g. stomach, duodenum, rectum, small intestine)
 - Largest lesion size ($\leq 10 \text{ cm or} > 10 \text{ cm}$)
 - Resectable (yes / no)
 - PDGFRA mutation status
 - Metastatic (yes / no)
 - Location of metastatic site(s)
- Relevant medical and surgical history including comorbidities and previous cancer diagnoses
- Prior imatinib therapy (yes / no)
- Duration of prior imatinib therapy
- Best response to prior imatinib therapy (CR, PR, SD, progressive disease, NE)
- Concomitant medications, with a special focus on CYP3A4 inhibitors/inducers to address the drug-drug interaction risk

The Medical Dictionary for Regulatory Activities (MedDRA) will be used for coding concomitant diseases, and the World Health Organization (WHO) Drug Dictionary for medications.

Avapritinib treatment details from the time of the first dose until 30 days after the last dose:

- Date of treatment initiation
- Primary reason for treatment initiation
- Setting (e.g. trial, CUP, EAP or routine care)
- Treatment schedule (e.g. qd, bid)

- Avapritinib treatment information: dose and dose modifications including date(s)
- Reason for dose modification
- Date of discontinuation or interruption
- Primary reason for discontinuation or interruption
- Reason for initiating further lines of treatment

Efficacy variables:

Efficacy data are of interest when collected prospectively or available from previous data collection efforts during standard of care visits at each site between the time of the first dose of avapritinib and the end of follow-up, ie, at least 24 months, until initiation of another treatment for GIST or until study discontinuation for any reason; whichever comes first. Survival is an exception and will be ascertained for all patients until study closure, which will occur when the last patient enrolled has been followed for at least 24 months or withdraws from the study for any reason.

The following efficacy data will be of interest:

• Date and details of tumour response and disease progression evaluations in accordance with mRECIST 1.1 when feasible or with local standard practice by the investigator

Safety variables:

All AEs that occur or have occurred during and/or up to 30 days after administration of avapritinib regardless of a causal relationship to avapritinib.

The following data will be collected for any AE (serious or non-serious):

- Date of event
- Event (all coded according to the same MedDRA version)
- Severity of event (classified using the National Cancer Institute Common Terminology Criteria for Adverse Events [NCI CTCAE] Version 5.0)
- Relationship to avapritinib
- Outcome (resolved, continuing, etc.)
- Action taken including description of types, severity and rates of AEs leading to avapritinib dose reductions, interruptions or discontinuations as well as medication used for AE treatment (coded according to the WHO Drug Dictionary)

Table 1:Data Collection Plan

Prospective Data Collection and Extraction of Available Retrospective Data				
Variables	Baseline Periodª	Standard of Care Visits ^b	Safety Follow-Up (Final Standard of Care Visit +30 days for all non- fatal AEs or study closure for deaths) ^c	Survival Follow-up (every 6 months

				until study closure)
Informed Consent ^d	Х			
Patient Eligibility	Х			
Demographics	Х			
Medical and Surgical History	Х			
Prior Imatinib Therapy (yes/no)	Х			
Concomitant Medications ^e	Х	X	Х	
Avapritinib Treatment Details	Х	X		
Disease Progression Evaluation by Investigator		Х		
Objective Response Evaluations by Investigator		Х		
Telephone contact				Xf
All AEs/SAEs	Х	X	Х	

Abbreviations: AE = adverse event; SAE = serious adverse event.

^a The baseline period includes the time up to and including the first avapritinib dose

^b Standard of care visits will be performed via telehealth or as in-person visits (study center or local clinic) in accordance with local standards. Data will be collected at least once per month during the first 3 months of avapritinib treatment where practical and every 2-3 months thereafter in accordance with local treatment guidelines.

^c Study closure will occur when the last patient enrolled has been followed for at least 24 months or withdraws from the study for any reason

^d According to the regulatory and legal country-specific requirements of the participating site. For those patients that have discontinued avapritinib treatment and/or were lost to follow-up and consent cannot be obtained, the Investigator will consult their IRB/IEC for guidance on accessing these patients' data retrospectively.

^e Information regarding concomitant medication (including over-the-counter medications) will include, when available: drug name, indication for treatment, route, and duration of drug administration, with a special focus on CYP3A4 inhibitors/inducers to address the drug-drug interaction risk

^fPatients will be followed for overall survival every 6 months until study closure. This follow-up can be completed via telephone.

9.4. Data Sources

For patients who initiate or continue to receive avapritinib in this study, data will be collected prospectively for 24 months following enrolment. For patients who have already received avapritinib prior to enrolment, retrospective data will also be collected (if available). Retrospective data collection will be performed at the participating investigator site through extraction of available data from the patient's medical records as per local law and regulations. Data will include: relevant baseline data at the time of the first dose of avapritinib and safety data from the time of the first dose of avapritinib to the end of follow-up, i.e. at least 24 months, until study discontinuation for any reason, or 30 days after the last dose of avapritinib; whichever comes first. In addition, data will include efficacy data (i.e. treatment response) between the first dose of avapritinib and the end of follow-up, i.e. at least 24 months, until initiation of second-line treatment or until study discontinuation for any reason; whichever comes first (see Table 1). Survival is an exception and will be ascertained for all patients until study closure, which will

occur when the last patient enrolled has been followed for at least 24 months, or withdraws from the study for any reason.

9.5. Study size

At least 50 patients are planned to be enrolled in this study. It is estimated that this number will be adequate to provide sufficient safety information in this ultra-rare patient population. If additional patients are available in a timely manner, more patients will be enrolled.

The sample size calculation is presented as follows: 'For patients with the PDGFRA D842V mutation, a sample size of 31 patients will allow testing the null hypothesis of ORR \leq 10% versus the alternative hypothesis of ORR \geq 35% using Fisher's exact test with 90% power assuming a 2-sided type I error rate of 0.05.'

9.6. Data management

All information outlined in Section 9.3 will either be recorded prospectively in an eCRF or extracted from patients' medical records for retrospective data collection, if data are available before the start of the study. Data collection will be completed in a suitable software platform for the creation and delivery of data collection, data analysis, and data reporting. Data collected will be stored at secure servers ensuring compliance with local or national regulations. Database lock is anticipated in August 2024 for an interim analysis and on the date the study is closed. Additional details regarding data collection and validation procedures will be detailed in a data management plan.

9.7. Data Analysis

The statistical analysis plan (SAP) provides further information to that discussed below (e.g. on handling missing data, correction of inconsistencies or errors, and differences in outcome definitions). The final analysis will conform to the analysis specifications provided in the SAP.

9.7.1. Analysis Populations

9.7.1.1. Enrolled Population (EP)

The enrolled population will consist of all patients who signed an informed consent.

9.7.1.2. Safety Population (SP)

The SP will include all patients enrolled in the study who met the eligibility criteria and received at least one dose of avapritinib. The SP will be the primary analysis population for the efficacy and safety analyses.

9.7.2. Statistical Methods

Descriptive analysis:

Demographic and other baseline characteristics collected before or at the time of the first avapritinib dose will be summarised for the SP. Continuous variables will be described (distribution) by their mean, standard deviation, median, extreme values (minimum and maximum) and the number of missing data. Categorical variables will be described using

frequency counts and percentages. Time-to-event data will be summarized by Kaplan-Meier (KM) estimates.

Analysis of the primary endpoint:

The primary endpoint for the study will be to describe AEs during the study period for the SP. Analyses will be conducted for the SP overall and stratified by treatment setting at the first dose of avapritinib and 300 mg dose, Eastern Cooperative Oncology Group (ECOG) performance status and country; feasibility requirements will be described in the SAP.

The study period for the safety analyses is defined as the time from the first dose of avapritinib to the end of follow-up, i.e. at least 24 months, until study discontinuation for any reason, or 30 days after the last dose of avapritinib; whichever comes first.

The following analyses will be performed:

- Number and proportions of patients experiencing an AE during the study period (i.e., from the first dose of avapritinib until the end of follow-up): by SOC (System Organ Class) and PT (Preferred Term) (MedDRA classification), severity, seriousness and relationship to avapritinib, including the description of types, severity and rates of AEs leading to discontinuation or decreased dosing of avapritinib.
- Number and proportions of patients with dose reductions or interruptions, or discontinuing avapritinib treatment due to an AE during the study period: overall and by comorbidity, including the description of types, severity and rates of AEs leading to discontinuation or decreased dosing of avapritinib.
- Incidence rate of patients experiencing an AE, overall and by SOC and PT terms
 - Defined as the number of patients with at least one (specific) AE during follow-up divided by the sum of person-months at risk in the study.
 - The sum of person-months at risk in the study when calculating the overall incidence is defined as the duration of follow-up for patients without AEs plus the duration of follow-up until the date of the first AE for patients with an AE.
 - The sum of person-months at risk in the study when calculating the incidence for specific AEs is defined as the duration of follow-up for patients without the specific AE plus the duration of follow-up from baseline until the date of the first specific AE for patients with a specific AE, i.e. patients who experience another AE earlier in time will not be censored

Specific safety concerns that will be reported, include but are not limited to:

- Intracranial bleeding (e.g. cerebral haematoma, cerebral haemorrhage, haemorrhage intracranial, subdural haematoma)
- Cognitive effects (e.g. agitation, amnesia, cognitive disorder, confusional state, delirium, dementia, disorientation, encephalopathy, hallucination, memory impairment, mental impairment, mental status changes, mood altered, personality change, psychotic disorder, somnolence, speech disorder)
- Drug-drug interactions with moderate or strong CYP3A4 inhibitors or inducers

- Cardiac toxicity (e.g. electrocardiogram QT interval abnormal, electrocardiogram QT prolonged long QT syndrome, long QT syndrome congenital, torsade de pointes, ventricular tachycardia, cardiac arrest, cardiac death, cardiac fibrillation, cardio-respiratory arrest, electrocardiogram repolarisation abnormality, electrocardiogram U wave inversion, electrocardiogram u wave present, electrocardiogram U-wave abnormality, loss of consciousness, multiple organ dysfunction syndrome, subacute kidney injury, sudden cardiac death, sudden death, syncope, ventricular arrhythmia, ventricular fibrillation, ventricular flutter, and ventricular tachyarrhythmia)
- Embryofoetal toxicity
- Any off-label use in patients with severe hepatic impairment (Child-Pugh class C, i.e. ≥ 10 points, Annex 3)
- Drug-drug interactions with CYP3A4 substrates

Analysis of the secondary endpoints:

Secondary endpoints will be described using the SP. Analyses will be conducted for the SP overall and avapritinib dose 300 mg, and may be stratified by treatment setting at the first dose of avapritinib (i.e. study BLU-285-1101, CUP/EAP, and routine care), Eastern Cooperative Oncology Group (ECOG) performance status and by country if feasible; feasibility requirements will be described in the SAP.

The study period for the efficacy analyses is defined as the time from the first dose of avapritinib to the end of follow-up at 24 months, until initiation of second-line treatment or until study discontinuation for any reason; whichever comes first. Survival is an exception and will be ascertained for all patients until study closure, which will occur when the last patient enrolled has been followed for at least 24 months or withdraws from the study for any reason. The analyses to be performed will be:

- Median, 95% CIs and 25th and 75th percentiles using the Kaplan-Meier (KM) method for:
 - OS
 - PFS
 - DoR
 - DoT
- OS rates at select timepoints
- ORR during the study period with 95% CI based on the exact binomial distribution

The following definitions will be used for the above outcomes:

- OS is defined as the time in months from the start of avapritinib treatment to the date of death due to any cause.
- PFS is defined as the time in months from the start of avapritinib treatment to the date of the first documented disease progression by a responsible physician according to mRECIST 1.1 criteria or local standard practice, or death.

- DoT is defined as the time from the date of the first to the date of the last avapritinib dose.
- DoR is defined as the time from the date of the first documented disease response to the date of disease progression.
- ORR is defined as the proportion of patients with a best response during the study period of complete response (CR) or partial response (PR) evaluated by a responsible physician based on mRECIST v1.1 criteria if feasible or to local standard practice.

An interim analysis is planned for an interim study report (data lock point in August 2024, submission interim report in February 2025). Details of the interim analysis will be described in the SAP.

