9.1. Study design

This is a multinational, open-label, observational PASS that will evaluate the long-term safety and efficacy of avapritinib in the first line or following ≤ 4 months of imatinib treatment in at least 50 patients with PDGFRA D842V-mutated GIST. Three patient populations are planned to be enrolled:

- Patients with PDGFRA D842V-mutated GIST who are scheduled to receive avapritinib in the first-line (or have received imatinib for ≤4 months)
- Patients with PDGFRA D842V-mutated GIST who are already receiving treatment with avapritinib (in the first-line or following ≤ 4 months of imatinib treatment)
- Patients with PDGFRA D842V-mutated GIST who previously received treatment with avapritinib in the first line or following ≤4 months of imatinib treatment and have discontinued treatment

In addition to evaluating safety and efficacy of first-line avapritinib treatment, patients who were initially treated with imatinib for \leq 4 months are also being in included this study to allow for practical, real-world, clinical experience with use of avapritinib in the PDGFRA D842V-mutated GIST population setting and increase the feasibility of study completion in this ultra-rare patient population.

Informed consent will be obtained from all patients according to the regulatory and legal country-specific requirements of the participating site before enrolment in this study.

Patients who were scheduled to receive avapritinib prior to enrolment will initiate treatment after enrolment in this study based on the locally approved product label prescribing information. If a patient was already receiving avapritinib prior to enrolment, they will continue treatment at the same dose after enrolment. The dose level may be adjusted based on the locally approved product label prescribing information. Investigators must refer to the local prescribing information for contraindications, warnings and precautions as well as use in specific populations. As this study is observational, the decision to treat patients with avapritinib will be independent from the decision to enrol patients into the study.

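### Pooling scheduled, ongoing and already-discontinued patients makes duration of treatment, and to a lesser degree AE-led discontinuation, depend on the recruitment mix

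*Protocol*

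**What the plan says.** Protocol 9.1: "Three patient populations are planned to be enrolled". They are patients "who are scheduled to receive avapritinib in the first-line", patients "who are already receiving treatment with avapritinib", and patients "who previously received treatment with avapritinib in the first line or following ≤4 months of imatinib treatment and have discontinued treatment". Prior imatinib of up to 4 months is allowed in each group.

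Protocol 9.7.1.2 puts all eligible, treated patients into one Safety Population: "The SP will be the primary analysis population for the efficacy and safety analyses".

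For the primary endpoint, 9.7.2 states: "Analyses will be conducted for the SP overall and stratified by treatment setting at the first dose of avapritinib and 300 mg dose", and adds ECOG status and country. Later in 9.7.2, treatment setting is spelled out as study BLU-285-1101, CUP/EAP or routine care. That is where the first dose was given, not whether the patient was still on drug at enrolment.

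Two listed outcomes turn on stopping:
- the proportion "discontinuing avapritinib treatment due to an AE during the study period", overall and by comorbidity;
- duration of treatment, summarised by Kaplan-Meier: "DoT is defined as the time from the date of the first to the date of the last avapritinib dose".

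On who gets in:
- 9.5 plans at least 50 patients and fixes no number per group.
- 9.9.1 promises consecutive invitation for newly enrolled patients only, and says that survivor bias will be avoided by including patients who had already stopped.
- 9.2.1 requires available retrospective data from discontinued patients.

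**The concern.** The variable that sorts patients into groups is also an outcome. Every patient in the discontinued group has stopped. No patient in the ongoing group stopped before enrolment, yet that patient's clock starts at first dose and 9.7.2 mentions no delayed entry. Only the scheduled group is unselected on stopping.

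If sites find ongoing patients more easily, the pooled duration of treatment is too long. If they find discontinued patients more easily, it is too short. This happens even when each enrolled patient is typical of his or her own group, and with no change in the drug's effect.

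AE-led discontinuation belongs to the primary objective. The study answers a Specific Obligation on first-line safety (8.1), and 9.9.1 plans to compare its AE rates with those of the earlier trials. A figure that moves with recruitment could look like a signal or hide one.

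**Working it through.** The protocol gives no figure for this point, so there is none to reproduce. The size is shown by an illustration.

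**Inputs from the protocol.** Three groups (9.1); about 50 patients (9.5); 24 months of prospective follow-up after enrolment for scheduled and ongoing patients (9.4); clock from first dose (9.7.2).

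**Assumptions, not in the documents.** Duration of treatment T is exponential with true median 24 months, so λ = ln 2 / 24 = 0.02888 per month. Of all stops, 40% are AE-led, independent of time. Patients who started before enrolment did so uniformly over the previous 60 months.

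**Natural split of earlier starters.**
- ∫₀⁶⁰ e^(−λa) da = (1 − e^(−60λ))/λ = 28.50.
- Still on treatment: 28.50/60 = 47.5%. Already stopped: 52.5%. The ratio is about 1 : 1.1.

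**AE-led discontinuation within 24 months of first dose, by group.**
- Scheduled: 0.40 × (1 − e^(−24λ)) = 0.40 × 0.50 = 20.0%. This is the truth.
- Ongoing: ∫₀²⁴ e^(−λa) da = 0.50/λ = 17.31. Chance of stopping by month 24 = (17.31 − 24 × 0.50)/28.50 = 0.186; × 0.40 = 7.5%.
- Discontinued: [(24 − 17.31) + 36 × 0.50]/(60 − 28.50) = 24.69/31.50 = 0.784; × 0.40 = 31.4%.

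**Pooled, n = 50** (scheduled/ongoing/discontinued):
- 20/25/5: (20 × 0.200 + 25 × 0.0745 + 5 × 0.3135)/50 = 14.9%, or 15%
- 20/10/20: (4.00 + 0.745 + 6.271)/50 = 22.0%, or 22%
- 10/10/30: (2.00 + 0.745 + 9.406)/50 = 24.3%, or 24%
- 20/14/16, close to the natural ratio: (4.00 + 1.044 + 5.017)/50 = 20.1%

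**Pooled Kaplan-Meier median duration of treatment from first dose, without delayed entry** (simulation, same assumptions, true value 24 months):

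| Mix | Median (months) |
|---|---|
| 20/25/5 | about 36 |
| 20/10/20 | about 21 |
| 10/10/30 | about 18 |
| 5/40/5 | about 44 |
| 20/14/16 | about 24 |

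Taken alone, ongoing patients give about 52 months and discontinued patients about 12.

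**Sensitivity.** With the 23.2-month median treatment duration that 7.1 reports for the Phase I trial as the true value, and 30% of stops AE-led, a 50/50/0 percentage mix gives 39 months, 50/25/25 gives 24 and 10/15/75 gives 15. Capturing every starter gives 23.1. With a true median of 36 months, 50/50/0 gives 58 and 10/15/75 gives 18.

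**Check of the remedy.** Scheduled plus ongoing patients, with ongoing patients entering the risk set at enrolment, give about 24 months in each mix tried (20/25, 20/10, 10/10 and 5/40).

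**The case against.** A reader might infer that the pooled figures are simply set by recruitment and estimate no patient's risk. The documents do not support that. Patients in the third group have all stopped, but not all for an AE. If ongoing and discontinued patients enter in their natural ratio, the pooled estimates are right, whatever the share of scheduled patients.

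A reader might also compare crude proportions over all follow-up. Under the same assumptions these are 20%, 20% and 40% by group, and so 22%, 28% and 32% for the first three mixes, against a 24-month truth of 20%. Most of that excess is longer follow-up. Even without selection, the crude figure among earlier starters is 0.475 × 20% + 0.525 × 40% = 30%. On a common 24-month horizon the bias is smaller, and for 20/25/5 it is downward. The exact 95% interval for 11/50 is 12% to 36%, which covers the whole 15% to 24% spread. Nor does the 12/56 (21%) in 7.1 corroborate the assumed 20%: it covers all lines of therapy at a data cutoff.

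Other safeguards can be cited:
- 9.9.3 allows further stratified or restricted analyses when deemed necessary, with treatment setting as an example only.
- 9.9.2 calls for sensitivity analyses on retrospective data, but because of data quality and missing data. It does not give the sponsor free control of the mix: it allows more new patients when retrospective data are poor, which tends to dilute the problem.
- An additional table split could sit in the SAP.

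These points lower the severity. They do not remove the finding, because 9.7.2 itself names the strata and defers only feasibility requirements to the SAP, and 9.9.1 states that survivor bias will be avoided.

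Finally, splitting by group is not enough. Ongoing and discontinued columns are conditioned on the outcome and are not risk estimates. That objection stands and shapes the fix.

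**Conclusion.** The point holds in a conditional form. Unless ongoing and discontinued patients are captured in proportion, which the protocol does not secure, pooled Kaplan-Meier duration of treatment depends materially on the recruitment mix: about 18 to 36 months against a true 24 in the three main mixes. AE-led discontinuation at 24 months depends on it less: 15% to 24% against 20%.

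These sizes rest on assumed exponential stopping, a 40% AE share, uniform earlier starts and chosen mixes. The direction of the bias follows from the group definitions, not from those values.

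This should be fixed, but it is not critical. The outcomes are descriptive, no hypothesis test rests on them, and AE-led discontinuation is one part of a broader primary objective.

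**What to change.** In 9.7.2:
- Show AE-led discontinuation, AE-led dose change and duration of treatment by enrolment group (scheduled, ongoing, discontinued before enrolment). State that this split is descriptive.
- Report AE-led discontinuation at a common time from first dose.
- Base the risk estimates for duration of treatment and discontinuation on scheduled plus ongoing patients, with ongoing patients entering the risk set at enrolment.
- Label the pooled figure as dependent on recruitment mix.

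In 9.9.1, replace the claim that survivor bias will be avoided with a statement that it is reduced only so far as all starters at a site are captured.

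Cost: a few sentences and extra table columns. Enrolment group and enrolment date are known for every patient, so no new data are needed. The downside is smaller numbers per column and wider intervals, and the discontinued group no longer contributes to the risk estimates, though it stays in the descriptive tables.

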Cognitive effects occurred in 182 (33%) of the 550 patients with GIST who received avapritinib at starting doses of either 300 or 400 mg once daily. Most cognitive effects were Grade 1 (89%), with Grade \geq 2 occurring in 11% of 550 patients. Memory impairment occurred in 20% of patients, <1% of these events were Grade 3. Cognitive disorder occurred in 12% of patients; <1% of these events were Grade 3. Confusional state occurred in 5% of patients; <1% of these events were Grade 3. Confusional state occurred in 5% of patients; <1% of these events were Grade 3. Encephalopathy occurred in <1% of patients; <1% of these events were Grade 3. SAEs of cognitive effects were reported for 7 of the 550 (1.3%) patients. Overall, 1.3% of patients required permanent discontinuation of avapritinib for a cognitive effect. Cognitive effects were reported by 46% of the patients in BLU-285-1101, most cases were mild-moderate AEs (90% Grade 1-2 AEs, 10% Grade 3 AEs). Consistent with the overall trend of a slightly less severe safety profile observed in the Phase III trial, cognitive effects were reported by 26% of the patients in BLU-285-1303, 95% Grade 1-2 AEs and 5% Grade 3 AEs. The early recognition and management of cognitive effects might explain the lower incidence in the Phase III trial as

AESIs of cognitive effects were higher in the 400 mg starting dose group compared to the 300 mg group in BLU-285-1101 (48% vs 39%). However, the median treatment duration for patients receiving avapritinib (any dose) in the Phase III trial was also considerably shorter (8.9 months) than in the Phase I trial (23.2 months). No fatal cognitive events were reported in either study. In the clinical development program, the probability of experiencing a cognitive effect increased over the first 7 to 8 months of treatment and then reached a plateau. Non-clinical mechanistic studies could not clearly identify the underlying mechanism for cognitive effects (i.e., memory impairment). Clinical factors associated with an increased likelihood of experiencing Grade \geq 2 cognitive effects include a medical history of cognitive effects, prior regorafenib use and age \geq 65 years. Brain imaging studies of patients experiencing cognitive effects effect symptoms during the clinical studies did not reveal any associated anatomical changes.

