Baseline and follow-up assessments will be in accordance with local standard medical care. Both prospective and retrospective data collection will be performed in this study. All patients who will initiate or continue treatment with avapritinib after enrolment will have prospective data collection for 24 months on the study. For patients who have received avapritinib prior to enrolment in this study, retrospective data may also be collected (if data are available). Retrospective data collection will be performed at the participating investigator site through extraction of available data from the patient's medical records. The data collection plan is provided in Table 1.

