9.9. Limitations of the Research Methods

9.9.1. Selection Bias

For patients who will be newly enrolled into this study, inviting consecutive patients at each site will reduce selection bias. In addition, AE rates obtained from this study will be compared with expected rates from the pooled analysis of AEs for all lines from the BLU-285-1101 and BLU-285-1303 trials. Survivor bias will be avoided (i.e. outcome ascertainment only for those who make it to the start of this study) by including patients who discontinued avapritinib treatment before enrolment in this study.

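### AE incidence and its comparison with the pooled trials are not aligned on time since first dose, so for cognitive effects the person-month rate mixes risk with length of follow-up

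*Protocol*

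**What the plan says.** **The rate.** Protocol section 9.7.2 gives the incidence rate as the "number of patients with at least one (specific) AE during follow-up divided by the sum of person-months at risk in the study". For a specific AE the denominator is "the duration of follow-up for patients without the specific AE plus the duration of follow-up from baseline until the date of the first specific AE" in those who have it. Numbers and proportions of patients with AEs are reported as well. The primary analyses are stratified by treatment setting at first dose, 300 mg dose, ECOG status and country. None of these splits is by time since first dose.

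**The window.** The same section sets the safety period as "the time from the first dose of avapritinib to the end of follow-up, i.e. at least 24 months", ended earlier by study discontinuation or by 30 days after the last dose. Section 9.1 adds that patients who start or continue treatment "will have prospective data collection for 24 months on the study", and retrospective time since first dose is added for those already treated. The window therefore differs in length from patient to patient.

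**The benchmark.** Section 9.9.1 states that "AE rates obtained from this study will be compared with expected rates from the pooled analysis of AEs for all lines" of BLU-285-1101 and BLU-285-1303. It does not say whether rates means person-month rates or percentages, and it sets no condition on exposure time or on patients who are in both data sets. Section 9.7.2 names BLU-285-1101 as one of the treatment settings.

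**The time course.** Section 7.1 reports that "the probability of experiencing a cognitive effect increased over the first 7 to 8 months of treatment and then reached a plateau". It gives median treatment of 23.2 months in BLU-285-1101 and 8.9 months in BLU-285-1303, and itself mentions this difference when it sets 46% with cognitive effects against 26%.

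**The concern.** Events over person-time is an average rate over the exposure observed. If the hazard is roughly constant, the average does not depend on how long patients are followed. If events stop after some months, each further month adds person-time from unaffected patients and no events, so the rate falls although risk has not changed. The protocol's own account of cognitive effects is of this second kind.

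Two readings are then at risk. Within the study, a whole-period average cannot show whether events continue, stop or appear late. Yet section 7.1 gives limited long-term data and longer first-line exposure as the uncertainty to be resolved. Against the benchmark, a lower or higher rate of an AESI could come from exposure length alone. A crude proportion does not solve this, because it has no time axis: it rises with follow-up until the plateau and does not show when events occurred.

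**Working it through.** **1. Figures from the documents (section 7.1).** Cognitive effects: 182/550 = 33.1%, which reproduces the stated 33%. Avapritinib patients: 250 in BLU-285-1101 and 239 + 96 = 335 in BLU-285-1303, total 585, as stated. Median treatment: 23.2 and 8.9 months.

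**2. Model (assumption).** The same risk everywhere: p = 0.33 by month 8, constant hazard until then and none afterwards. Medians are treated as fixed follow-up T.

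- Hazard to month 8: λ = −ln(0.67)/8 = 0.0501 per month.
- Person-months per patient, for T of 8 or more: 0.33/λ + 0.67 × (T − 8) = 6.592 + 0.67 × (T − 8).
- Rate as defined in 9.7.2: 0.33 divided by that.

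| T (months) | Person-months per patient | Rate per 100 person-months |
|---|---|---|
| 8.9 | 7.195 | 4.59 |
| 23.2 | 16.776 | 1.97 |
| 24 | 17.312 | 1.91 |
| 36 | 25.352 | 1.30 |
| 48 | 33.392 | 0.99 |

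**3. The planned comparison.** Pooled trials: events 0.33 × 585 = 193.05; person-months 250 × 16.776 + 335 × 7.195 = 6,604; rate 2.92 per 100.

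- Against 24 months here: 2.92/1.906 = 1.53.
- Against 48 months here: 2.92/0.988 = 2.96 (2.9 if the rounded rates 2.9 and 1.0 are divided).
- The two agree only if follow-up here is about 15 months: 6,604/585 = 11.29 person-months per patient, and 8 + (11.29 − 6.59)/0.67 = 15.0. With shorter follow-up the bias reverses, and this study would look worse.

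**4. Is 48 months possible?** For some patients. Someone dosed in BLU-285-1101 before the 9 March 2020 cutoff, enrolled from Q4 2022 and still on treatment brings nearly 31 retrospective months plus 24 prospective, about 55. As an average for the whole study, 48 months is an upper illustration.

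**5. Sensitivity.** The 8.9 versus 23.2 month ratio is 2.3 to 2.4 for a plateau at month 7 or 8, 2.2 with p = 0.46, and 2.0 to 2.1 if follow-up is exponential with those medians.

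**6. Check on the reported trial results.** A constant hazard with medians as fixed follow-up gives −ln(0.54)/23.2 = 2.7 per 100 person-months for BLU-285-1101 (46%) and −ln(0.74)/8.9 = 3.4 for BLU-285-1303 (26%). The trial with more patients affected gets the lower rate. The 1303 hazard carried to 23.2 months would predict 1 − 0.74^(23.2/8.9) = 54%, against the 46% seen.

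**7. A time-aligned measure.** In the model, cumulative incidence at any fixed time after month 8 is 33% whatever the follow-up. The interval rate is 5.0 per 100 person-months to month 8 and zero after.

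**8. Shared patients.** Section 7.1 counts 11 first-line D842V patients in BLU-285-1101. That is at most 11/50 = 22% of the minimum study size and 11/585 = 1.9% of the comparator.

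**The case against.** The strongest reply has four parts.

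- **The study is descriptive and does not rest on one number.** Proportions are reported, the analyses are stratified, and the treatment-setting stratum isolates BLU-285-1101 patients. This stands: what is absent is a split by time. Stratifying by setting does not supply one.
- **Detail belongs to the SAP, and section 9.7.2 already says that time-to-event data will be summarised by Kaplan-Meier.** This stands for the choice of estimator, time points and handling of competing events. But the rate formula is fixed in the protocol, and the outcomes listed for Kaplan-Meier are OS, PFS, DoR and DoT, not AEs.
- **Section 9.9.1 does not say that person-month rates are compared, and the pooled figures in section 7.1 are percentages.** Correct. The factors above apply if person-month rates are used. If percentages are used, the two sides still lack a common exposure time. The undefined scale is part of the point.
- **The plateau is reported for cognitive effects only.** Correct. No time course is given for intracranial bleeding or for AEs in general, so the calculation does not carry over to them.

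A reader might also infer that person-time runs to study closure, because survival is followed that long. Section 9.7.2 does not support this: it ends the safety period no later than 30 days after the last dose, and follow-up to closure is an exception for survival.

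**Conclusion.** The point holds for cognitive effects and for the comparison in section 9.9.1. With the same true risk, the planned person-month rate would look about 1.5-fold lower in this study than in the pooled trials at 24 months of follow-up, and up to about 3-fold lower at 48. This rests on a 33% risk complete by month 8, medians used as fixed follow-up, and person-month rates being what 9.9.1 compares. If patients here stay on treatment for less than about 15 months, the distortion runs the other way.

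Three stronger readings are not supported. First, the rate does not reflect follow-up instead of risk; it reflects both. At 24 months a 46% risk gives 3.15 and a 33% risk 1.91 per 100 person-months, a ratio of 1.65. Second, setting 8.9 against 48 months gives 4.59/0.988 = 4.6-fold, but the protocol plans no such comparison. Third, shared BLU-285-1101 patients do not materially move the comparator, of which they are under 2%. They matter because up to 22% of the minimum sample here would be compared with a pool that contains them, and eligibility may make that share smaller.

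This is an inexpensive improvement. It does not invalidate the primary analysis.

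**What to change.** - **Section 9.7.2:** keep the planned rate and proportions. For the AESIs, at least cognitive effects, add cumulative incidence at fixed times since first dose, or rates by interval since first dose with a cut near the reported plateau. The estimator, the time points and the handling of death and end of treatment can be set in the SAP.
- **Section 9.9.1:** state the scale of the AE rates, compare at matched exposure times, and leave out of that comparison patients whose first dose was in BLU-285-1101. They stay in all other analyses.

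**Cost.** Some extra programming on AE and dosing dates that section 9.3 already collects; access to the sponsor's own trial data at the matching times; and a smaller sample for the comparison, at worst 50 − 11 = 39 patients at the minimum study size.
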